**Table 34: Absolute Change in FEV1 from Baseline by Treatment Group – ITT Population, Stage 2a and 2b**

[Implementation note: ‘Selected Dose’ will be replaced with the dose chosen by the interim analysis].

Time Point	Treatment Group	FEV1 (liters)					Change from Baseline (liters)					
		n	Mean	SD	Median	Min, Max	n	Mean	SD	Median	Min, Max	95% CI a
Baseline	Selected Dose (N=X)	x	xx.x	xx.x	xx.x	xx.x, xx.x	-	-	-	-	-	-
	Placebo (N=X)	x	xx.x	xx.x	xx.x	xx.x, xx.x	-	-	-	-	-	-
Day 1 Post-infusion	Selected Dose (N=X)	x	xx.x	xx.x	xx.x	xx.x, xx.x	x	xx.x	xx.x	xx.x	xx.x, xx.x	xx.x, xx.x
	Placebo (N=X)	x	xx.x	xx.x	xx.x	xx.x, xx.x	x	xx.x	xx.x	xx.x	xx.x, xx.x	xx.x, xx.x
Day 2	Selected Dose (N=X)	x	xx.x	xx.x	xx.x	xx.x, xx.x	x	xx.x	xx.x	xx.x	xx.x, xx.x	xx.x, xx.x
	Placebo (N=X)	x	xx.x	xx.x	xx.x	xx.x, xx.x	x	xx.x	xx.x	xx.x	xx.x, xx.x	xx.x, xx.x
Day 5	Selected Dose (N=X)	x	xx.x	xx.x	xx.x	xx.x, xx.x	x	xx.x	xx.x	xx.x	xx.x, xx.x	xx.x, xx.x
	Placebo (N=X)	x	xx.x	xx.x	xx.x	xx.x, xx.x	x	xx.x	xx.x	xx.x	xx.x, xx.x	xx.x, xx.x
Day 30	Selected Dose (N=X)	x	xx.x	xx.x	xx.x	xx.x, xx.x	x	xx.x	xx.x	xx.x	xx.x, xx.x	xx.x, xx.x
	Placebo (N=X)	x	xx.x	xx.x	xx.x	xx.x, xx.x	x	xx.x	xx.x	xx.x	xx.x, xx.x	xx.x, xx.x
Maximum	Selected Dose (N=X)	x	xx.x	xx.x	xx.x	xx.x, xx.x	x	xx.x	xx.x	xx.x	xx.x, xx.x	xx.x, xx.x
	Placebo (N=X)	x	xx.x	xx.x	xx.x	xx.x, xx.x	x	xx.x	xx.x	xx.x	xx.x, xx.x	xx.x, xx.x

Notes: N=Number of subjects in the ITT population in Stage 2a and 2b.

n=Number of subjects in the ITT Population with non-missing FEV1 measurements at the time point of interest. For the change from baseline, n represents the number of subjects in the ITT population with non-missing values at baseline and at the time point being assessed.

SD=Standard Deviation

Baseline is defined as the last measurement taken prior to dosing on Study Day 1.

a95%CI is calculated from a t-distribution.

Maximum	Selected Dose (N=X)	x	xx.x	xx.x	xx	xx, xx	xx, xx	xx, xx	xx.x	xx.x	xx	xx, xx	xx, xx	x.xx, x.xx	
	Placebo (N=X)	x	xx.x	xx.x	xx	xx, xx	xx, xx	xx, xx	xx.x	xx.x	xx	xx, xx	xx, xx	x.xx, x.xx	
[Repeat for all morphologies]															

Notes: N=Number of subjects in the ITT population in Stage 2a and 2b.

n=Number of subjects in the ITT population in Stage 2a and 2b with non-missing colony counts at the time point of interest. For the change from baseline, n represents the number of subjects in the ITT population with non-missing values at baseline and at the time point being assessed.

SD=Standard Deviation

Baseline is defined as the last measurement taken prior to dosing on Study Day 1.

aQ1 and Q3 represent the 25th and 75th percentiles, respectivelyb95%CI is calculated from a t-distribution.

**Table 37: Proportion of *P. aeruginosa* Isolates Susceptible to Individual Bacteriophages – ITT Population, Stage 2a and 2b**

[Implementation note: ‘Selected Dose’ will be replaced with the dose chosen by the interim analysis. If multiple timepoints are collected, then this table will be stratified by timepoint with an additional ‘All Timepoints’ category.]

P. aeruginosa Isolate	Selected IV Bacteriophage Dose				Placebo				Difference 95% CI b
	N	n	%	95% CI a	N	n	%	95% CI a	
[Bacteriophage 1]									
[Isolate 1]	x	x	x	(x.x, x.x)	x	x	x	(x.x, x.x)	xx (x.x, x.x)
[Isolate 2]	x	x	x	(x.x, x.x)	x	x	x	(x.x, x.x)	xx (x.x, x.x)
[Isolate 3]	x	x	x	(x.x, x.x)	x	x	x	(x.x, x.x)	xx (x.x, x.x)
[Isolate 4]	x	x	x	(x.x, x.x)	x	x	x	(x.x, x.x)	xx (x.x, x.x)
[Repeat for each bacteriophage]									

Notes: *P. aeruginosa* isolate will be identified by individual morphotype ID.

N=Number of subjects in the ITT population in Stage 2a and 2b with non-missing values for isolate susceptibility.

n=Number of subjects with isolates susceptible to the corresponding bacteriophage.

a95% CI for proportions calculated using the Wilson method.

b95% CI for the difference in proportions, IV bacteriophage relative to placebo, calculated using the Miettinen–Nurminen method.

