- ***P. aeruginosa* colony counts** will be performed by the central lab using quantitative bacterial cultures on sputum specimens collected from the time of bacteriophage administration through Day 30 ± 7 days. Quantities of sputum (10 mg) will be measured precisely and added to 1 mL Sputolysin mucolytic agent to liquefy the sample. The liquefied sample will be diluted sequentially and plated onto MacConkey agar and Sheep's Blood Agar Plates using a 1 μ L loop for each replicate. Colonies will be counted on the highest dilution in which individual colonies can be enumerated and colony counts adjusted appropriately based on the dilution factor and the mass of the sample to determine the true concentration of *P. aeruginosa*. Colonies representing different morphotypes will be definitively identified using MALDI-TOF to ensure that each enumerated colony type represents *P. aeruginosa*. Refer to the MOP for additional details.
- ***P. aeruginosa* susceptibility to bacteriophages** may be performed by the central lab on *P. aeruginosa* isolates in sputum cultures, depending on sample availability.

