##### **3.1.3. Exploratory**

- Characterize the serum and sputum pharmacokinetic (PK) profiles of a single dose of IV bacteriophage therapy in clinically stable CF subjects with *P. aeruginosa* in expectorated sputum.
- Describe changes in lung function from the administration of a single dose of IV bacteriophage therapy through Day  $30 \pm 7$ .
- Characterize geographically diverse *P. aeruginosa* isolates susceptibility to bacteriophages.
- Describe subjects' quality of life (QoL) before and after receiving bacteriophage therapy.

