## 4.6. Exploratory Endpoint Variables

There will be four exploratory objectives: (1) characterize the serum and sputum PK profiles of a single dose of IV bacteriophage therapy in clinically stable CF subjects with *P. aeruginosa* in expectorated sputum, (2) change in lung function from the administration of a single dose of IV bacteriophage therapy through Day  $30 \pm 7$ , (3) characterize geographically diverse *P. aeruginosa* isolates susceptibility to bacteriophages, and (4) describe subjects' QoL before and after receiving bacteriophages. The SAP for the first exploratory objective, related to serum and sputum PK, will be provided in a separate document.

Change in lung function will be measured using FEV1. Spirometry will be performed at screening, baseline, and at follow-up visits occurring on Days 2, 5, 12, and 30.

Phage susceptibility testing (PST) will occur using a plaque assay and the liquid assay. These assays describe the proportion of *P. aeruginosa* isolates that are susceptible to each phage and to the phage cocktail. Both the plaque assay and liquid assay will be evaluated every time sputum is obtained (see schedule of study

procedures in [Table 1](#)). An isolate will be considered susceptible to phage if both the plaque assay and the liquid assay indicate susceptibility.

The CFQ-R (<https://cfqr-app.netlify.app/#/questionnaire>) is a self-administered QoL questionnaire designed to measure the impact that CF has on overall health, daily life, and perceived well-being and symptoms. The CFQ-R contains 50 items and will be administered at in-person and virtual study visits for Stage 2 subjects. The CFRSD (<https://depts.washington.edu/seaqol/CFRSD-CRISS>) is a subject reported outcome measure that is used to evaluate the effect of treatment on respiratory infection symptom severity in patients with CF and chronic respiratory infection. Quality of Life will be measured using the CFQ-R and the CFRSD. The CFQ-R will be administered at baseline and at the final follow-up visit (Day  $30 \pm 7$ ). The CFRSD will be administered at baseline and at follow-up visits occurring on Day 2, 5, 8, and 30.

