**Table 1: Schedule of Study Procedures (continued)**

Visit	Screening	Baseline/Dosing	Follow-up Visits					Early Termination Visit  /Unscheduled Study Visit
Visit Number	1	2	3	4	5	6	7	N/A
Day (Window)	Up to Day -7	1	2	5 ± 2	8 + 3	12 + 7	30 ± 7	Variable
CFRSD (Stage 2 only) 		X 	X	X	X		X	X
Safety Assessment		X	X	X	X	X	X	X
Events of Special Interest		X	X	X	X			X 

Abbreviations: CFQ-R: Cystic fibrosis questionnaire-revised; CFRSD: Cystic fibrosis respiratory symptom diary; HCG: Human chorionic gonadotropin; N/A: Not Applicable; PK: Pharmacokinetic

May be conducted by telephone call if subject is too ill to attend in-person or virtual visit, per local investigator.

Pregnancy testing will be performed for all female subjects of childbearing potential and the results of both the HCG test at screening and urine test at baseline must be negative prior to treatment assignment/randomization.

Including full account of the subject's routine respiratory physiotherapy regimen.

Medication history within the past 30 days and those that remain active.

Standard of care results obtained for clinical care purposes within 72 hours of screening are acceptable for screening.

Before administration of study product or placebo AND 30-60 minutes after completed administration of study product or placebo.

Spirometry to occur prior to study product/placebo administration and within 30 minutes to 2 hours after study product/placebo administration.

If the visit occurs > 7 days after a scheduled visit. If the visit occurs ≤ 7 days after a scheduled visit, spirometry may be performed at the discretion of the local investigator.

At in-person visits. To be completed after spirometry, as considered necessary by the local investigator to increase sputum production.

Sputum will be obtained pre-infusion and post-infusion for microbiological and PK assessments (refer to the protocol, Sections 7.2.1 and 7.2.2 for details).

Standard of care labs obtained within 7 days of Baseline may be used to record these results, otherwise, assessments must be done as a study procedure.

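### SAP Table 37 gives no pooled pre-dose estimate of phage susceptibility, and its All Timepoints category has no defined unit or collapsing rule

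*SAP*

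**What the plan says.** The exploratory objective in SAP 3.1.3 is to "Characterize geographically diverse" *P. aeruginosa* isolates by their susceptibility to the phages. The matching endpoint in SAP 3.2.3 is a proportion of susceptible isolates, for each phage and for the cocktail. It names no comparison between arms.

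On how often susceptibility is tested, SAP 4.6 says: "Both the plaque assay and liquid assay will be evaluated every time sputum is obtained". Protocol 7.2.2 is softer and makes testing optional, "depending on sample availability". The schedule (SAP Table 1) provides samples on both sides of dosing: "Sputum will be obtained pre-infusion and post-infusion for microbiological and PK assessments".

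SAP Table 37 has a selected-dose column and a placebo column, each with N, n, a percentage and a Wilson interval. A further column gives a "95% CI for the difference in proportions, IV bacteriophage relative to placebo", by the Miettinen–Nurminen method. There is no all-subjects column. On time, the note reads: "If multiple timepoints are collected, then this table will be stratified by timepoint with an additional" category, All Timepoints.

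The units conflict. The table notes count people: "N=Number of subjects in the ITT population in Stage 2a and 2b with non-missing values for isolate susceptibility" and "n=Number of subjects with isolates susceptible to the corresponding bacteriophage". The table title and SAP 8.2.2 speak of isolates, and the rows are morphotypes within phage. SAP 8.2.2 also announces the table as presented by dose, but the shell carries one dose.

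**The concern.** Two things are at issue.

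**Who is included.** A pre-dose isolate is susceptible or not before its host is assigned to anything. Splitting the pre-dose stratum by arm, with a between-arm difference, divides one population in two and measures chance imbalance. The objective asks for one description of that population. The table also drops the 16 Stage 2a subjects on the unselected doses and the 6 sentinels, although Protocol 10.5.7 assigns sentinel sputum to exploratory analysis.

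**What All Timepoints means.** If SAP 4.6 is followed, the condition in the note is met and the category appears. It then combines samples taken before and after phage exposure. Nothing says how a subject who is susceptible at one visit and resistant at another enters it.

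Subjects are not screened for susceptibility before dosing, and SAP 6.4 names susceptibility as the only pre-specified subgroup. A reader interpreting a weak microbiological result will want to know how often the cocktail could have acted at all.

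**Working it through.** The documents give no expected proportion or target precision for susceptibility, so there is no planned figure to reproduce.

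**Subject counts.**
- Per arm: 8 + 12 = 20 to 8 + 17 = 25.
- Two arms summed: 40 to 50.
- All Stage 2: 32 + 24 = 56 to 32 + 34 = 66.
- All enrolled: 6 + 56 = 62 to 6 + 66 = 72.
- Stage 2a subjects on dropped doses: 2 × 8 = 16.

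**Precision of a pre-dose proportion.** The Wilson half-width is z·√(p(1−p)/n + z²/4n²) / (1 + z²/n), with z = 1.96. Assume p = 0.6 and one result per subject. At n = 20: 1.96 × √(0.0120 + 0.0024) / 1.192 = 0.197.

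| Subjects used | n | Half-width, points |
|---|---|---|
| One arm | 20 / 25 | 19.7 / 17.9 |
| Two columns summed | 40 / 50 | 14.5 / 13.1 |
| All Stage 2 | 56 / 66 | 12.4 / 11.5 |
| All enrolled | 62 / 72 | 11.8 / 11.0 |

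Over p = 0.3 to 0.9, summing the two arms cuts the interval width by about 26% to 30%. Using all Stage 2 subjects cuts it by about 36% to 41%. Every n here is an upper limit. Testing depends on sample availability, the SAP addendum reports 3 of 32 Stage 2a subjects with undetectable counts at baseline, and morphotype rows divide the subjects further.

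**All Timepoints.** A Stage 2 subject has up to seven sputum samples: Screening and Day 1 pre-infusion before dosing, then Day 1 post-infusion and Days 2, 5, 8 and 30. Five of seven are post-dose, or five of six without Screening. The two possible units behave differently.

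*Subjects counted once, as the notes say.* Simulated coverage of the nominal 95% Wilson interval is 92% to 98% (20 or 25 subjects, true proportion 0.5 to 0.9). The interval is adequate, but the quantity depends on an unstated rule. Take a beta-binomial model with mean 0.7, within-subject correlation (ICC) 0.5 and six samples, which gives beta parameters 0.7 and 0.3:
- Any sample susceptible: 1 − (0.3 × 1.3 × 2.3 × 3.3 × 4.3 × 5.3)/720 = 1 − 0.094 = 91%.
- All samples susceptible: (0.7 × 1.7 × 2.7 × 3.7 × 4.7 × 5.7)/720 = 44%.

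The same data would report 91% or 44%, with no treatment effect assumed.

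*Samples counted.* Treat 6 or 7 samples from each of 20 or 25 subjects as independent (20,000 simulated trials, true proportion 0.5 to 0.9). Coverage is about 93% to 96% at ICC 0, 79% to 86% at 0.2, 64% to 73% at 0.5 and 53% to 65% at 0.8. Only on this reading are the intervals too narrow.

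**The case against.** The two-column layout follows a stated convention. SAP 6.1 and Section 8 compare selected dose with placebo in all microbiological tables. Because subjects are not screened for susceptibility, showing chance imbalance between arms has some use. The timepoint strata already isolate a clean pre-dose result in each arm. Both columns print N and n, so a reader can add them within a row. That reaches 13 to 15 points, and going on to everyone enrolled gains only a further 2 to 3 (14.5 to 11.8, or 13.1 to 11.0). Susceptibility results also go to Listing 13, whose mock-up shows a subject on a dose that was not selected, so those results are not lost.

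All of this stands, and it limits the severity. It does not supply the estimate that the objective asks for. A reader can sum the columns but cannot recover the 22 omitted subjects from the table. Nor does any of it define All Timepoints.

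**Conclusion.** The point holds as a minor one. Table 37 lacks a pooled pre-dose estimate that needs no extra data. At an assumed 60% susceptibility, the half-width could fall from 18–20 points per arm to 11–12 with everyone enrolled and tested. All Timepoints mixes pre- and post-dose results and has no collapsing rule, so its estimand is undefined. The 91% and 44% figures rest on an assumed 70% susceptibility and ICC of 0.5.

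A reader might infer three stronger things that the documents do not support:
- *That the table's intervals are invalid.* The notes count subjects, and on that count coverage is adequate. Undercoverage arises only if samples are counted.
- *That the pooled row will be biased by resistance after dosing.* This needs a post-dose change in the phage arm. The protocol names resistance kinetics as a knowledge gap but gives no rate, and with no change there is no shift.
- *That the table hides emerging resistance behind a headline row.* Nothing makes All Timepoints the main result, and the by-arm post-dose strata would show a loss of susceptibility.

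The endpoint is exploratory and no primary result depends on Table 37.

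**What to change.** Add to Table 37 a pre-dose panel using the Day 1 pre-infusion isolate, or Screening if that is missing. Pool it over all enrolled subjects with a result: Stage 1, all four Stage 2a arms and Stage 2b. Give one proportion and Wilson interval per phage and one for the cocktail, with no arm contrast. State in one sentence how a subject with several morphotypes is counted.

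Keep the by-arm, by-timepoint strata for post-dose results. Delete All Timepoints, or state its unit and collapsing rule and use a subject-clustered interval.

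The cost is some SAP wording and one extra panel, with no new data. Sentinels are not randomised, which does not matter for a pre-dose proportion. Leaving them out would cost only about half a point of half-width (12.4 against 11.8, or 11.5 against 11.0).

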**Table 38: Change from Baseline of QoL Score, CFQ-R Questionnaire – ITT Population, Stage 2a and 2b**

[Implementation note: ‘Selected Dose’ will be replaced with the dose chosen by the interim analysis.

The following domains will be included: Physical, Role, Vitality, Emotion, Social, Body, Eat, Treat, Health, Weight, Respiration, Digestion, Sinus, and Overall. The Overall score for each subject will be calculated as the sum of the combined domain scores.]

Time Point	Treatment Group	QoL Score					Change from Baseline						
		n	Mean	SD	Median	Min, Max	n	Mean	SD	Median	Min, Max	95% CI a	
Physical													
Baseline	Selected Dose (N=X)	x	xx.x	xx.x	xx	xx, xx	-	-	-	-	-	-	-
	Placebo (N=X)	x	xx.x	xx.x	xx	xx, xx	-	-	-	-	-	-	-
Day 30	Selected Dose (N=X)	x	xx.x	xx.x	xx	xx, xx	x	xx.x	xx.x	xx	xx, xx	x.xx, x.xx	
	Placebo (N=X)	x	xx.x	xx.x	xx	xx, xx	x	xx.x	xx.x	xx	xx, xx	x.xx, x.xx	
...													
[Repeat for all domains]													

Notes: N=Number of subjects in the ITT population in Stage 2a and 2b.

n=Number of subjects in the ITT population in Stage 2a and 2b with non-missing QoL scores at the time point of interest. For the change from baseline, n represents the number of subjects in the ITT population in Stage 2a and 2b with non-missing values at baseline and at the time point being assessed.

SD=Standard Deviation

Baseline is defined as the last measurement taken prior to dosing on Study Day 1.

a95% CI will be calculated from a t-distribution.

**Table 39: Change from Baseline of QoL Score, CFRSD Questionnaire – ITT Population, Stage 2a and 2b**

[Implementation note: ‘Selected Dose’ will be replaced with the dose chosen by the interim analysis.]

Time Point	Treatment Group	Total QoL Score					Change from Baseline					
		n	Mean	SD	Median	Min, Max	n	Mean	SD	Median	Min, Max	95% CI a
Baseline	Selected Dose (N=X)	x	XX.X	XX.X	XX	XX, XX	-	-	-	-	-	-
	Placebo (N=X)	x	XX.X	XX.X	XX	XX, XX	-	-	-	-	-	-
Day 2	Selected Dose (N=X)	x	XX.X	XX.X	XX	XX, XX	x	XX.X	XX.X	XX	XX, XX	X.XX, X.XX
	Placebo (N=X)	x	XX.X	XX.X	XX	XX, XX	x	XX.X	XX.X	XX	XX, XX	X.XX, X.XX
Day 5	Selected Dose (N=X)	x	XX.X	XX.X	XX	XX, XX	x	XX.X	XX.X	XX	XX, XX	X.XX, X.XX
	Placebo (N=X)	x	XX.X	XX.X	XX	XX, XX	x	XX.X	XX.X	XX	XX, XX	X.XX, X.XX
Day 8	Selected Dose (N=X)	x	XX.X	XX.X	XX	XX, XX	xx	XX.X	XX.X	XX	XX, XX	X.XX, X.XX
	Placebo (N=X)	x	XX.X	XX.X	XX	XX, XX	xx	XX.X	XX.X	XX	XX, XX	X.XX, X.XX
Day 30	Selected Dose (N=X)	x	XX.X	XX.X	XX	XX, XX	xx	XX.X	XX.X	XX	XX, XX	X.XX, X.XX
	Placebo (N=X)	x	XX.X	XX.X	XX	XX, XX	x	XX.X	XX.X	XX	XX, XX	X.XX, X.XX
Maximum	Selected Dose (N=X)	x	XX.X	XX.X	XX	XX, XX	xx	XX.X	XX.X	XX	XX, XX	X.XX, X.XX
	Placebo (N=X)	x	XX.X	XX.X	XX	XX, XX	x	XX.X	XX.X	XX	XX, XX	X.XX, X.XX

Notes: N=Number of subjects in the ITT population in Stage 2a and 2b.

n=Number of subjects in the ITT population in Stage 2a and 2b with non-missing QoL score at the time point of interest. For the change from baseline, n represents the number of subjects in the ITT population in Stage 2a and 2b with non-missing values at baseline and at the time point being assessed.

SD=Standard Deviation

Baseline is defined as the last measurement taken prior to dosing on Study Day 1.

\*95% CI is calculated from a t-distribution.

## 14.3 Safety Data

### 14.3.1 Displays of Adverse Events

**Table 40: Overall Summary of Adverse Events**

Subjects meeting at least one of the below conditions	4x10  PFU Dose (N=X)		4x10  PFU Dose (N=X)		4x10  PFU Dose (N=X)		Placebo (N=X)		All Subjects (N=X)	
	n	%	n	%	n	%	n	%	n	%
Stage 1										
At least one adverse event	x	xx	x	xx	x	x	x	xx	x	xx
At least one related adverse event	x	x	x	x	x	x	x	x	x	x
At least one mild (or worse) related adverse event	x	x	x	x	x	x	x	x	x	x
At least one moderate (or worse) related adverse event	x	x	x	x	x	x	x	x	x	x
At least one severe related adverse event	x	x	x	x	x	x	x	x	x	x
At least one serious adverse event	x	x	x	x	x	x	x	x	x	x
At least one related, serious adverse event	x	x	x	x	x	x	x	x	x	x
At least one adverse event leading to early termination	x	x	x	x	x	x	x	x	x	x
Stage 2a										
...										
Stage 2a and 2b										
...										

Note: N=Number of subjects in the Safety Population

**Table 41: Adverse Events Occurring in 5% of Subjects in Any Treatment Group by MedDRA System Organ Class, High Level Term, Preferred Term, and Treatment Group, Stage 1 – Safety Population**

MedDRA System Organ Class	MedDRA High Level Term	MedDRA Preferred Term	4x10  PFU Dose (N=X)			4x10  PFU Dose (N=X)			4x10  PFU Dose (N=X)			Placebo (N=X)			All Subjects (N=X)		
			n	%	Events	n	%	Events	n	%	Events	n	%	Events	n	%	Events
Serious Adverse Events																	
All	All	All	x	x	x	x	x	x	x	x	x	x	x	x	x	x	x
SOC1	HLT1	PT1	x	x	x	x	x	x	x	x	x	x	x	x	x	x	x
Etc.	Etc.	Etc.															
Other (Non-serious) Adverse Events																	
All	All	All	x	x	x	x	x	x	x	x	x	x	x	x	x	x	x
SOC1	HLT1	PT1	x	x	x	x	x	x	x	x	x	x	x	x	x	x	x
Etc	Etc.	Etc															

Notes: N=Number of subjects in the Safety Population.

n=Number of subjects reporting event.

Events=Total frequency of events reported.

**Table 42: Adverse Events Occurring in 5% of Subjects in Any Treatment Group by MedDRA System Organ Class, Preferred Term, and Treatment Group, Stage 2a – Safety Population****Table 43: Adverse Events Occurring in 5% of Subjects in Any Treatment Group by MedDRA System Organ Class, Preferred Term, and Treatment Group, Stage 2a and 2b – Safety Population**

**Table 44: Summary of Grade 2 or Higher Treatment Emergent AEs by MedDRA System Organ Class, High Level Term, Preferred Term, and Treatment Group – ITT Population**

[Implementation Note: If there is only 1 PT for an SOC, there will be no “Any PT” row.

Treatment group order: All subjects,  $4 \times 10^7$  PFU Dose,  $4 \times 10^8$  PFU Dose,  $4 \times 10^9$  PFU Dose, Placebo]

Treatment Group	MedDRA System Organ Class	MedDRA High Level Term	MedDRA Preferred Term	N	n (%)	95% CI a	Number of Events
All Subjects (N=X)	Any SOC	Any HLT	Any PT	x	x (x)	xx, xx	x
	[SOC 1]	Any HLT	Any PT	x	x (x)	xx, xx	x
		[HLT 1]	Any PT	x	x (x)	xx, xx	x
			[PT 1]	x	x (x)	xx, xx	x
	[SOC 2]	Any HLT	Any PT	x	x (x)	xx, xx	x
		[HLT 1]	Any PT	x	x (x)	xx, xx	x
			[PT 1]	x	x (x)	xx, xx	x
$4 \times 10^7$ PFU Dose (N=X)	...		...	x	x (x)	xx, xx	x
	...		...	x	x (x)	xx, xx	x
Placebo (N=X)	...		...	x	x (x)	xx, xx	x

Notes: N=Number of subjects in the ITT population in the specified Treatment Group.

n=Number of subjects with Grade 2 or higher treatment-emergent AEs.

A subject is only counted once per PT per treatment group and study part.

aExact Clopper-Pearson Confidence Interval.

**Table 45: Difference in Proportion of Grade 2 or Higher Treatment Emergent AEs in IV Bacteriophage vs. Placebo – ITT Population**

[Implementation Note: If there is only 1 PT for an SOC, there will be no “Any PT” row. This table will compare the Selected Dose of IV Bacteriophage to Placebo.]

MedDRA System Organ Class	MedDRA High Level Term	MedDRA Preferred Term	IV Bacteriophage n(%)	Placebo n(%)	Difference in Proportion	95% CI a
Any SOC	Any HLT	Any PT	x (x)	x (x)	x	xx, xx
[SOC 1]	Any HLT	Any PT	x (x)	x (x)	x	xx, xx
	[HLT 1]	Any PT	x (x)	x (x)	x	xx, xx
		[PT 1]	x (x)	x (x)	x	xx, xx
[SOC 2]	Any HLT	Any PT	x (x)	x (x)	x	xx, xx
	[HLT 1]	Any PT	x (x)	x (x)	x	xx, xx
		[PT 1]	x (x)	x (x)	x	xx, xx
...		...	x (x)	x (x)	x	xx, xx
...		...	x (x)	x (x)	x	xx, xx
...		...	x (x)	x (x)	x	xx, xx

Notes: n=Number of subjects with Grade 2 or higher treatment-emergent AEs.

A subject is only counted once per PT per treatment group and study part.

a95% CI for the difference in proportions, IV bacteriophage relative to placebo, calculated using the Miettinen–Nurminen method.

**14.3.1.2 Unsolicited Adverse Events****Table 46: Summary of Unsolicited Adverse Events by MedDRA System Organ Class, High Level Term, Preferred Term, and Treatment Group, Stage 1 – Safety Population**

[Implementation Note: If there is only 1 PT for an SOC, there will be no “Any PT” row.

Treatment group order: All subjects,  $4 \times 10^7$  PFU Dose,  $4 \times 10^8$  PFU Dose,  $4 \times 10^9$  PFU Dose, Placebo.]

Treatment Group	MedDRA System Organ Class	MedDRA High Level Term	MedDRA Preferred Term	N	n (%)	95% CI a	Number of Events
All Subjects (N=X)	Any SOC	Any HLT	Any PT	x	x (x)	xx, xx	x
	[SOC 1]	Any HLT	Any PT	x	x (x)	xx, xx	x
		[HLT 1]	Any PT	x	x (x)	xx, xx	x
			[PT 1]	x	x (x)	xx, xx	x
	[SOC 2]	Any HLT	Any PT	x	x (x)	xx, xx	x
		[HLT 1]	Any PT	x	x (x)	xx, xx	x
			[PT 1]	x	x (x)	xx, xx	x
4 $\times$ 10  PFU Dose (N=X)	...		...	x	x (x)	xx, xx	x
...	...		...	x	x (x)	xx, xx	x
Placebo (N=X)	...		...	x	x (x)	xx, xx	x

Notes: N=number of subjects in the Safety Population in the specified Treatment Group.

A subject is only counted once per PT per treatment group and study part.

aExact Clopper-Pearson Confidence Interval.

**Table 47: Summary of Unsolicited Adverse Events by MedDRA System Organ Class, Preferred Term, and Treatment Group, Stage 2a – Safety Population****Table 48: Summary of Unsolicited Adverse Events by MedDRA System Organ Class, Preferred Term, and Treatment Group, Stage 2a and 2b – Safety Population**

**Table 49: Unsolicited Adverse Events by MedDRA System Organ Class, High Level Term, Preferred Term, Maximum Severity, Relationship, and Treatment Group, Stage 1 – Safety Population**[Implementation Note: Treatment group order: All subjects,  $4 \times 10^7$  PFU Dose,  $4 \times 10^8$  PFU Dose,  $4 \times 10^9$  PFU Dose, Placebo.]

Treatment Group	MedDRA System Organ Class	MedDRA High Level Term	MedDRA Preferred Term	Severity	Related n (%)	Not Related n (%)	Total n (%)
All Subjects (N=X)	Any SOC	Any HLT	Any PT	Any Severity	x (%)	x (%)	x (%)
				Mild	x (%)	x (%)	x (%)
				Moderate	x (%)	x (%)	x (%)
				Severe	x (%)	x (%)	x (%)
	[SOC 1]	Any HLT	Any PT	Any Severity	x (%)	x (%)	x (%)
				...	x (%)	x (%)	x (%)
			[PT 1]	Any Severity	x (%)	x (%)	x (%)
				...	x (%)	x (%)	x (%)
$4 \times 10^7$ PFU Dose (N=X)	Any SOC		Any PT	Any Severity	x (%)	x (%)	x (%)
...	...		...	...	x (%)	x (%)	x (%)
Placebo (N=X)	...		...	...	x (%)	x (%)	x (%)

Notes: N=Number of subjects in the Safety Population in each Treatment Group.

Subjects are only counted once per PT and treatment group, in the highest reported severity.

**Table 50: Unsolicited Adverse Events by MedDRA System Organ Class and Preferred Term, Maximum Severity, Relationship, and Treatment Group, Stage 2a – Safety Population****Table 51: Unsolicited Adverse Events by MedDRA System Organ Class and Preferred Term, Maximum Severity, Relationship, and Treatment Group, Stage 2a and 2b – Safety Population**

**Table 52: Summary of TEAEs, On-Therapy SAEs, and AEs Leading to Discontinuation by MedDRA Preferred Term, and Treatment Group, Stage 1 – Safety Population**

[Implementation note: Sort this table by decreasing frequency for ‘All Subjects’.]

Preferred Term	4x10  PFU Dose (N=X)			4x10  PFU Dose (N=X)			4x10  PFU Dose (N=X)			Placebo (N=X)			All Subjects (N=X)		
	n	%	Events	n	%	Events	n	%	Events	n	%	Events	n	%	Events
Treatment-Emergent AEs															
All	x	x	x	x	x	x	x	x	x	x	x	x	x	x	x
PT1	x	x	x	x	x	x	x	x	x	x	x	x	x	x	x
PT2	x	x	x	x	x	x	x	x	x	x	x	x	x	x	x
Etc	x	x	x	x	x	x	x	x	x	x	x	x	x	x	x
...	x	x	x	x	x	x	x	x	x	x	x	x	x	x	x
On-Therapy AEs															
...	x	x	x	x	x	x	x	x	x	x	x	x	x	x	x
AEs Leading to Discontinuation															

Note: N=Number of subjects in the Safety Population.

**Table 53: Summary of TEAEs, On-Therapy SAEs, and AEs Leading to Discontinuation by MedDRA Preferred Term, and Treatment Group, Stage 2a – Safety Population****Table 54: Summary of TEAEs, On-Therapy SAEs, and AEs Leading to Discontinuation by MedDRA Preferred Term, and Treatment Group, Stage 2a and 2b – Safety Population**

